14.3 Vital Signs and Weight

Vital signs will be collected throughout the study. Weight and BMI will be observed and/or derived at Screening Visit 1, Baseline (Week 0) and Visit 6 (Week 4/EOT/ET). Observed values and the changes from Baseline at each post-Baseline visit will be summarized by treatment group using descriptive statistics.

Vital sign and weight values will be considered PCI if they meet the criteria listed in [Table 4](#). The number and percentage of subjects with post-Baseline vital signs and weight that are PCI will be

summarized by treatment group at each post-Baseline visit and for overall post-Baseline. For the overall post-Baseline summaries, all post-Baseline values will be considered, including unscheduled and out of window values. Subjects with multiple PCI values for a given parameter will be counted only once for that parameter. For the by-visit summary, the numerator for the percentage is the number of subjects with a post-Baseline PCI value for the given parameter, visit and treatment group, and the denominator is the number of subjects with non-missing values for the given parameter, visit and treatment group. For the overall post-Baseline summary, the numerator for the percentage is the number of subjects with at least 1 post-Baseline PCI value for the given parameter and treatment group, and the denominator is the number of subjects with at least 1 post-Baseline value for the given parameter and treatment group. A listing of subjects with any PCI value will be provided.

Table 4 Criteria for Potentially Clinically Important (PCI) Vital Signs and Weight

Vital Sign Parameter	Unit	Criteria		
		Observed Value	And/Or	Change Relative to Baseline
Systolic blood pressure (supine or sitting)	mmHg	≥180	And	Increase of ≥20
		≤90	And	Decrease of ≥20
Diastolic blood pressure (supine or sitting)	mmHg	≥105	And	Increase of ≥15
		≤50	And	Decrease of ≥15
Pulse (supine or sitting)	bpm	≥120	And	Increase of ≥15
		≤50	And	Decrease of ≥15
Weight	kg	Not Applicable		Increase of ≥7%
				Decrease of ≥7%

14.4 **Electrocardiogram (ECG)**

12-lead ECGs are collected throughout the study. Observed values of ECG variables (e.g., heart rate, PR interval, QRS interval, QT interval, and QTc interval) and the changes from Baseline at each assessment time point will be summarized by treatment group.

QTcF will also be categorized into the following categories (msec) and the number and percentage of subjects in each category will be summarized by treatment group at each visit and for the overall post-Baseline maximum:

- Observed: ≤450, 451 - ≤480, 481 - ≤500, and >500; >450; >480.
- Change from Baseline: ≤10, 11 – 30, 31 – 60, and >60; >30.

Electrocardiogram variable values will be considered PCI if they meet the criteria listed in Table 5. The number and percentage of subjects with post-baseline PCI values will be summarized by treatment group at each post-Baseline visit and for overall post-Baseline. For the by-visit summary, the numerator for the percentage is the number of subjects with a post-Baseline PCI ECG for the given parameter, visit and treatment group, and the denominator is the number of subjects with non-missing values for the given parameter, visit and treatment group. For the overall post-Baseline summary, the numerator for the percentage is the number of subjects with at least 1 post-Baseline PCI ECG for the given parameter and treatment group, and the denominator is the number of subjects with at least 1 post-Baseline ECG value for the given parameter and treatment group. A listing of all subjects with any PCI value will be provided.

Table 5 Criteria for Potentially Clinically Important ECG Values

ECG Parameter	Unit	High PCI Criteria
QRS Interval	msec	≥120
PR Interval	msec	≥220
QTcB or QTcF	msec	>500
QTcB or QTcF: change from baseline	>60 msec	

Cardiologist interpretations (normal and abnormal) will be summarized in a frequency table by treatment group and visit and for overall post-Baseline.

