1.2.2 Quetiapine

Quetiapine is a second-generation antipsychotic that has affinity for D₂, 5-HT_{2A}, H₁, alpha 1 and 5-HT_{1A} receptors. Its precise mechanism of action is unknown, but according to the dopamine theory of schizophrenia, antipsychotic effects might be related to the drug's ability to reduce dopaminergic neurotransmission in the mesolimbic pathway.

Quetiapine immediate-release is an orally administered antipsychotic approved in the United States for the treatment of schizophrenia, acute treatment of manic episodes associated with bipolar I disorder, depressive episodes associated with bipolar disorder, and maintenance treatment of bipolar I disorder ([Northstar Rx LLC. 2019](#)). The extended-release formulation is approved in the US for use as adjunctive treatment to antidepressant therapy of major depressive disorder. Quetiapine is also commonly used in off-label indications such as behavioral and psychological symptoms of dementia, posttraumatic stress disorder, depression psychosis in Parkinson's disease, anxiety disorders and insomnia ([El-Saifi et al. 2016](#)). In randomized controlled trials that recruited relatively younger and healthier populations, as opposed to the patients prescribed the medication in clinical

practice, the most frequent quetiapine side effects included somnolence (18%), dizziness (11%), dry mouth (9%), constipation (8%), orthostatic hypotension (4%), weight gain (5%), and lethargy dyspepsia (5%) ([El-Saifi et al. 2016](#)).

In April 2005, the US Food and Drug Administration (FDA) issued a warning about the increased risk of mortality associated with the use of second-generation antipsychotics in older adults with dementia-related psychosis, based on the analyses of 17 placebo-controlled trials. Most of the deaths were cardiovascular (e.g., heart failure, sudden death) or infectious (e.g., pneumonia) in nature. The quetiapine prescribing information also includes a warning regarding QT prolongation.

Additional information is provided in the US package insert for quetiapine ([Northstar Rx LLC 2019](#)).

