27. Is judged by the Investigator or the Medical Monitor to be inappropriate for the study for any reason, including if the subject is judged to be a danger to self or others
28. Has orthostatic hypotension at Screening or Baseline. A drop in systolic BP of ≥ 20 mm Hg, or in diastolic BP of ≥ 10 mm Hg, within 3 minutes of standing, or experiencing significant lightheadedness or dizziness after standing, along with a remarkable drop in BP as judged by the Investigator with agreement of the Sponsor's Medical Monitor, is considered orthostatic hypotension.

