6.3.2 Vital Signs

Vital signs will include body temperature, resting respiration rate, systolic and diastolic blood pressure, and pulse rate.

Each time vital signs are measured the following procedures for orthostatic blood pressure (BP) and pulse rate (PR) evaluation should be followed:

- After the subject is supine for approximately 5 minutes, BP and PR will be measured and the subject will then be instructed to rise to a standing position if able. Then BP and PR will again be measured 1-3 minutes after standing. A drop in systolic BP of ≥ 20 mm Hg, or in diastolic BP of ≥ 10 mm Hg, within 3 minutes of standing, or experiencing

significant lightheadedness or dizziness after standing, along with a remarkable drop in BP as judged by the Investigator with agreement of the Sponsor's Medical Monitor, is considered orthostatic hypotension. Patients who have orthostatic hypotension at Screening (Visit 1) or Baseline (Visit 2) are not eligible for the study.

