9.5.3 Other Safety Analyses

The serum clinical chemistry, hematology, and urinalysis results at each time point will be summarized by treatment group. Change from Baseline values will also be summarized.

The number and percentage of subjects with potentially clinically important (PCI) post-Baseline laboratory values will be summarized by treatment group at each post-Baseline visit and overall post Baseline for selected parameters. The PCI criteria will be specified in the statistical analysis plan.

Vital signs and body weight at Baseline and each post-Baseline visit will be summarized by treatment group. Change from Baseline values will also be summarized.

The results of the physical examinations at each visit will be tabulated by treatment group.

Electrocardiogram parameters at study visits will be summarized by treatment group. Change from Baseline values will also be summarized. Categorical analyses will be conducted on the incidence of subjects with prolonged QTc intervals and changes in QTc intervals in accordance with ICH guidelines.

For the C-SSRS, the number and percentage of subjects with suicidal ideation or suicidal behavior during the study will be tabulated.

MDS UPDRS Part III observed value and change from Baseline to Week 4 will be summarized by treatment group. The change from Baseline to Week 4 in the MDS UPDRS Part III score will be analyzed using an analysis of covariance (ANCOVA) model with treatment group as a factor and the Baseline value as a covariate.

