20.2 Supplementary Tables

Table 6 Schedule of Events and Assessments

	Screening	Baseline	Double-blind Treatment Period				Safety Follow-up
Visit Week (Study Day)	-4	0	1 (Day 7)	2 (Day 14)	3 (Day 21)	4/EOT (Day 28)	8 ¹ (Day 58)
Visit Number	1	2	3	4	5	6/ET	7
Visit window (days)	0	0	±3	±3	±3	±3	±4
Type of Visit	Clinic	Clinic	Clinic	Clinic	Clinic	Clinic	Telephone
Informed consent	X						
Inclusion/exclusion criteria	X	X					
Medical history and demographics	X						
Psychiatric and neurological history	X						
Physical examination (including neurologic examination)	X	X				X	
Training on the use of the handheld device and the actigraph ^a	X	X					
Orthostatic vital signs	X	X	X	X	X	X	
Weight and BMI ^b	X	X					X
Height	X						
12-lead ECG ^c	X	X	X	X	X	X	
Clinical laboratory tests	X	X		X			X
Pregnancy test ^d	X	X					X
Urine drug screen	X	X ^k					X
Capsule swallowing test ^e	X						
MMSE	X						
Dispense study drug ^g		X	X	X	X		
CGI-S ^f	X	X					
Trail Making Test ^f		X	X	X			X
HVLT-R ^f		X	X	X			X
Handheld device questionnaires ^h		X-----X					
Actigraphy data collection ⁱ		X-----X					
PD NMS Questionnaire ^f		X	X	X	X		
PGI-I ^f			X	X	X		X
CGI-I ^f			X	X	X		X
MDS UPDRS ^f		X					X
Subject and Informant satisfaction question			X	X	X	X	
Concomitant medications	X	X	X	X	X	X	X
C-SSRS ^{f,j}	X	X	X	X	X	X	

	Screening	Baseline	Double-blind Treatment Period				Safety Follow-up
Visit Week (Study Day)	-4	0	1 (Day 7)	2 (Day 14)	3 (Day 21)	4/EOT (Day 28)	8 ¹ (Day 58)
Visit Number	1	2	3	4	5	6/ET	7
Visit window (days)	0	0	±3	±3	±3	±3	±4
Type of Visit	Clinic	Clinic	Clinic	Clinic	Clinic	Clinic	Telephone
Assessment of adverse events	X	X	X	X	X	X	X
Study drug accountability			X	X	X	X	

Abbreviations: CGI-I=Clinical Global Impression-Improvement; CGI-S=Clinical Global Impression-Severity; C-SSRS=Columbia-Suicide Severity Rating Scale; ECG=electrocardiogram; EOT=end of treatment; ET=early termination; HVLT-R=Hopkins Verbal Learning Test-Revised; MDS UPDRS=Movement Disorders Society Unified Parkinson's Disease Rating Scale; MMSE=Mini-Mental State Examination; PD NMS=Parkinson's Disease Non-motor Symptoms; PGI-I=Patient Global Impression-Improvement

- a Training on the handheld device and actigraph may be done on the first day of Screening but must take place at least 7 days before the Baseline visit.
- b Measurement of weight and BMI are required at Screening and Baseline; measurement of weight (not BMI) is required at Week 4/EOT.

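### SAP Table 4 uses no standing reading and no supine-to-standing difference, so measured postural falls get no by-arm count, although the paired readings are scheduled at every clinic visit

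*SAP*

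**What the plan says.** **Collection.** Protocol 6.3.2 states: "Each time vital signs are measured the following procedures for orthostatic blood pressure (BP) and pulse rate (PR) evaluation should be followed". Supine readings come first, after about 5 minutes. The subject then stands, if able, and "Then BP and PR will again be measured 1-3 minutes after standing". Protocol Table S-1 and SAP Table 6 both carry a row "Orthostatic vital signs" marked at Visits 1 to 6, four of which are post-Baseline.

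**Definition.** Protocol 6.3.2 gives numeric limits for orthostatic hypotension: a systolic fall of at least 20 mm Hg or a diastolic fall of at least 10 mm Hg within 3 minutes of standing. It adds a limb based on symptoms and investigator judgement. The protocol applies the definition to eligibility. Exclusion criterion 28 begins "Has orthostatic hypotension at Screening or Baseline".

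**Analysis.** SAP 14.3 says "Observed values and the changes from Baseline at each post-Baseline visit will be summarized by treatment group using descriptive statistics", without naming a posture or a postural difference. Its PCI criteria are in Table 4, where the systolic row reads "Systolic blood pressure (supine or sitting"; the diastolic and pulse rows carry the same posture label. Each of these criteria joins an absolute limit to a change from Baseline with And. The low limits are systolic 90 or less with a decrease of at least 20, and diastolic 50 or less with a decrease of at least 15.

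**The concern.** The primary objective is safety and tolerability of pimavanserin and low-dose quetiapine against placebo. Protocol 1.2.2 includes orthostatic hypotension, at 4%, in its list of the most frequent quetiapine side effects. That figure comes from trials in relatively younger and healthier people. The study measures the postural response at every clinic visit, yet the SAP text turns none of those pairs into a by-arm result.

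The remaining by-arm route is the TEAE tables of SAP 14.1. An abnormal sign can qualify as an adverse event under protocol 7.1.1, but the visit enquiry in protocol 7.4.1 is a nonspecific question. A measured fall without symptoms therefore enters a table only if the investigator chooses to record it. A count of measured falls would complement the TEAE incidence. It is a different quantity from an adverse event rate.

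**Working it through.** The plan states no figure on this point to reproduce. The check sets the two rules side by side and then asks whether other parts of the plan fill the gap.

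**1. The rules.** Let S0 be the Baseline supine value, S1 the supine value at a visit and T1 the standing value at that visit.

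| Rule | Systolic | Diastolic |
|---|---|---|
| Protocol 6.3.2, numeric part | S1 − T1 ≥ 20 | S1 − T1 ≥ 10 |
| SAP Table 4, low criterion | S1 ≤ 90 and S0 − S1 ≥ 20 | S1 ≤ 50 and S0 − S1 ≥ 15 |

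T1 does not appear in the Table 4 rule. If S1 = S0, the change is 0 and no blood pressure criterion can be met, whatever T1 is. A subject with a postural fall can still be flagged on a supine or sitting reading, but that flag does not come from the fall.

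**2. One subject (illustrative values).** Supine 130/80 at Baseline and at the visit; standing 100/65 at the visit.
- Protocol: falls of 130 − 100 = 30 and 80 − 65 = 15, so the numeric definition is met.
- Table 4: supine 130/80 with change 0/0, so no flag.

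**3. Would adding standing values to the existing rows be enough?** Take unchanged supine Baseline as the reference. The fall needed for a flag is then max(20, supine − 90) systolic and max(15, supine − 50) diastolic. The supine values below are assumptions.

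| Supine systolic | Fall needed | Supine diastolic | Fall needed |
|---|---|---|---|
| 110 | 20 | 60 | 15 |
| 120 | 30 | 70 | 20 |
| 130 | 40 | 75 | 25 |
| 140 | 50 | 80 | 30 |

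The protocol thresholds are 20 and 10. Relabelling alone would miss many qualifying falls, including the subject in step 2.

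**4. Would descriptive statistics by posture show it?** They need not, even if standing values are included. Take a constructed arm of 4, systolic only:
- Baseline supine 120, 120, 130, 130; standing 115, 115, 125, 125.
- Visit supine 110, 120, 130, 140 in both scenarios.
- Scenario A, standing 95, 105, 115, 125: falls 15, 15, 15, 15, so 0 of 4 meet the systolic limit.
- Scenario B, standing 105, 95, 125, 115: falls 5, 25, 5, 25, so 2 of 4 meet it.

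In both scenarios the standing values have mean 110, SD √(500/3) = 12.91 and range 95 to 125. The standing changes from Baseline have mean −10, SD √(200/3) = 8.16 and range −20 to 0. The supine statistics are also the same. The mean change of −10 is visible but does not separate 0 of 4 from 2 of 4. This shows that masking is possible, not that it is likely.

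**5. Size.** SAP 19 gives 11 randomized subjects, so there are at most 4 × 11 = 44 scheduled post-Baseline pairs. The split by arm is not stated; a near-even split, assumed here, gives 3 or 4 per arm. Exact 95% intervals for an arm of 4 are 0 to 60% for 0/4 (upper limit 1 − 0.025^(1/4) = 0.602) and 7 to 93% for 2/4.

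**The case against.** The strongest reply is that nothing promised has been left out. A reader might infer that the SAP breaks a protocol commitment. The documents do not support that: protocol 9.5.3 says only "Vital signs and body weight at Baseline and each post-Baseline visit will be summarized by treatment group", with change from Baseline, and it promises PCI counts for laboratory values alone. Table 4 already goes beyond it.

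A reader might also infer that postural falls go unreported. That is too strong. SAP 5 lists all data apart from actigraphy and handheld-device data, so up to 44 pairs could be subtracted by hand. Recorded adverse events enter the TEAE tables. SAP 1 places table, figure and listing specifications in a separate document, which might contain an orthostatic table. The point therefore concerns the SAP text only.

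Third, the protocol uses its definition for eligibility and never names it as a post-Baseline outcome. Its last clause, on a remarkable fall judged by the investigator with the Medical Monitor's agreement, may qualify only the symptom limb or every limb. Using the numeric part as a descriptive row is an analyst's choice and must be declared as such.

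All three replies stand as limits. None supplies a by-arm count of measured falls in the SAP.

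**Conclusion.** The gap in the SAP text is real and modest. Following SAP 14.3 as written gives no by-arm count of measured supine-to-standing falls, and a fall with unchanged supine pressure contributes zero to the PCI table at any size. This follows from the Table 4 labels and needs no assumption. The arm sizes in the working are assumed.

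Two further inferences should be resisted. With 11 subjects, the count would support no comparison between arms, and no test or estimate in the plan changes. Also, because of exclusion 28, a post-Baseline case in an eligible subject was not present at Screening or Baseline, but that alone does not show a new condition or a drug effect. The value is descriptive, in a pilot meant to inform later designs. The change is worth making because it is cheap.

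**What to change.** In SAP 14.3:
- Derive standing-minus-supine systolic and diastolic pressure at each visit.
- Add one descriptive PCI row using the numeric thresholds of protocol 6.3.2 (systolic fall ≥ 20 or diastolic fall ≥ 10 mm Hg within 3 minutes of standing). State that the protocol uses this definition for eligibility and that the row applies the numeric limb without the investigator-judgement clause.
- Report n (%) by arm, per visit and overall post-Baseline, among subjects with both readings. Report the number with a missing standing reading beside it, because this denominator drops anyone unable to stand.
- Footnote that symptomatic cases are counted only if recorded as adverse events, that the timing of the pairs relative to the in-clinic dose is not specified (the post-dose timing footnote in SAP Table 6 is not attached to this row), and that the row does not replace the TEAE incidence.
- Align the Table 4 posture label with the postures measured, since protocol 6.3.2 describes supine and standing readings but no sitting reading.

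The cost is SAP wording and one derived parameter set from data already collected. If outputs are final, one supplementary table is enough. The downside is one more small table, with about 3 to 4 subjects per arm under a near-even split, which may mix pre-dose and post-dose readings.

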4.2 Exclusion Criteria

A subject must meet none of the following exclusion criteria to be eligible for the study:

1. Has atypical parkinsonism (Parkinson's plus, multiple system atrophy [MSA], progressive supranuclear palsy [PSP]), or secondary parkinsonism variants such as tardive or medication-induced parkinsonism
2. Has undergone ablative procedures such as a pallidotomy, thalamotomy, or treatment with focused ultrasound
3. Is in hospice, is receiving end-of-life palliative care, or is bedridden or confined to a wheelchair (as defined by spending >80% of the day in a wheelchair)
4. Has neuropsychiatric symptoms that are primarily attributable to current delirium or substance abuse
5. Has current evidence of an unstable neurological, cardiovascular, respiratory, gastrointestinal, renal, hepatic, hematologic, or other medical or psychiatric disorder, including cancer or malignancies that, in the judgment of the Investigator, would jeopardize the safe participation of the subject in the study or significantly interfere with the conduct or interpretation of the study
6. Has a history of epilepsy
7. Has atrial fibrillation unless adequately anticoagulated
8. Has a history of myocardial infarction, unstable angina, acute coronary syndrome, or cerebrovascular accident within the last 6 months prior to Visit 1 (Screening)
9. Has any of the following:
 - a. greater than New York Heart Association (NYHA) Class 2 congestive heart failure
 - b. Grade 2 or greater angina pectoris (by Canadian Cardiovascular Society Angina Grading Scale)
 - c. sustained ventricular tachycardia
 - d. ventricular fibrillation
 - e. torsades de pointes
 - f. syncope due to an arrhythmia
 - g. an implantable cardiac defibrillator
10. Has a known history of a positive hepatitis B virus (HBV) or hepatitis C virus (HCV) test
11. Has a history of human immunodeficiency virus (HIV)

12. Has a history of neuroleptic malignant syndrome or serotonin syndrome
13. Has a known personal or family history of long QT syndrome or family history of sudden cardiac death
14. Has any of the following electrocardiogram (ECG) results at the Screening or Baseline visit:
 - a. If the subject is **not** on citalopram, escitalopram, or venlafaxine:
 - i. QTcF >450 ms, if QRS duration <120 ms
 - ii. QTcF >470 ms, if QRS duration \geq 120 ms
 - b. If the subject is on citalopram, escitalopram, or venlafaxine:
 - i. QTcF >425 ms, if QRS duration <120 ms
 - ii. QTcF >450 ms, if QRS duration \geq 120 ms

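### SAP Table 5 counts QRS and PR values as potentially clinically important without regard to Baseline, although subjects already at or above the QRS cut-off may enrol

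*SAP*

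**What the plan says.** SAP Section 14.4 states that "Electrocardiogram variable values will be considered PCI if they meet the criteria listed in Table 5". Two rows of Table 5 are absolute thresholds with no reference to Baseline: "QRS Interval msec ≥120" and "PR Interval msec ≥220". The only change-based row concerns QTc: "QTcB or QTcF: change from baseline", set at more than 60 ms.

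The percentage over all post-Baseline visits is defined thus: "the numerator for the percentage is the number of subjects with at least 1 post-Baseline PCI ECG for the given parameter and treatment group". Everyone in the arm with any post-Baseline value for that parameter goes into the denominator. The by-visit summary is built the same way, on subjects with a non-missing value at that visit. Neither summary removes, or shows separately, subjects who already met the criterion at Baseline.

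Protocol exclusion 14 (Synopsis and Section 4.2) sets its QTcF limit according to QRS duration. For subjects not on citalopram, escitalopram or venlafaxine, one excluding condition is "QTcF >470 ms, if QRS duration \geq 120 ms". For subjects on one of those drugs the corresponding limit is 450 ms. A QRS of 120 ms or more is thus allowed at entry when QTcF is within the limit. No exclusion criterion names the PR interval.

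Elsewhere the SAP does refer to Baseline. Table 4 in Section 14.3 has a column headed "Change Relative to Baseline"; for blood pressure and pulse a value must meet both the threshold and a change. Section 14.2 gives laboratory values shift tables against Baseline. No ECG shift table is specified.

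**The concern.** The entry criteria and the PCI rule use the same QRS figure, 120 ms. The protocol expressly provides for subjects on the far side of that line, and the SAP then counts each of them as having a post-Baseline PCI value. Such a subject can be counted at each of the four post-Baseline ECG visits (Weeks 1 to 4) and in the overall row, with no change on treatment. The count therefore mixes findings that arose after dosing with findings that were there before it.

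The study's primary objective is safety and tolerability against placebo, and the arms ended up very small. One pre-existing conduction finding can dominate an arm's QRS percentage, and the table would not show that it was pre-existing. For PR the evidence is weaker: it is only that nothing in the entry criteria keeps out subjects already at 220 ms or more.

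**Working it through.** The plan states no figure to reproduce. The check has three parts.

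**1. Apply the rule to example QRS pairs (Baseline, then post-Baseline).**

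| Baseline (ms) | Post-Baseline (ms) | Counted under Table 5 (post ≥120) | Counted as new (post ≥120 and Baseline <120) |
|---|---|---|---|
| 130 | 130 | yes | no |
| 130 | 124 | yes | no |
| 110 | 122 | yes | yes |
| 100 | 110 | no | no |

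The first two rows are the problem: no change, and an improvement, are both counted.

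**2. Effect of one such subject on an arm's percentage.** SAP Section 19 gives 11 subjects randomized. Allocation is 1:1:1, so arms of 3 or 4 are assumed (11/3 = 3.7); the documents do not give the actual split. The planned size is 60/3 = 20 per arm. All subjects are assumed to have a post-Baseline ECG.

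- Arm of 3: 1/3 = 33.3 points
- Arm of 4: 1/4 = 25.0 points
- Arm of 20: 1/20 = 5.0 points

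**3. Chance that at least one such subject is present.** The documents give no prevalence of QRS ≥120 ms among entrants, so the share p is an assumption, shown over a range. Formula: 1 − (1 − p)^n.

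| Assumed p | n = 3 | n = 4 | n = 11 |
|---|---|---|---|
| 1% | 3.0% | 3.9% | 10.5% |
| 2% | 5.9% | 7.8% | 19.9% |
| 5% | 14.3% | 18.5% | 43.1% |
| 10% | 27.1% | 34.4% | 68.6% |

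For example, 1 − 0.95^4 = 0.185 and 1 − 0.95^11 = 0.431. The n = 11 column is the chance that some arm is affected; the n = 3 and n = 4 columns are for one given arm. No similar calculation is offered for PR.

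**The case against.** The strongest reply is that little depends on this table. The primary endpoint is treatment-emergent adverse events. Protocol Section 7.1.1 does not treat a stable pre-existing condition as an adverse event, and SAP Section 14.1 keeps Day 1 pre-dose ECG findings out of the treatment-emergent count. No test is planned on PCI counts, and Protocol Section 9.2 disclaims definitive comparisons. SAP Section 14.4 also summarizes change from Baseline for PR and QRS, lists every subject with a PCI value, and tabulates the cardiologist's readings; SAP Section 5 lists all data other than actigraphy and handheld data. With 11 subjects, each PCI entry can be traced to its Baseline value. Moreover, absolute PCI thresholds are not peculiar to QRS and PR: the laboratory criteria in Tables 2 and 3 have no Baseline condition either.

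Most of this stands and limits the weight of the point, but it does not repair the table. Group summaries of change do not show which PCI subjects are new, and matching listings by hand is not a planned output. Laboratory values have shift tables to compensate (on normal ranges, not PCI cut-offs), whereas ECG values have none.

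A second objection concerns the remedy. Simply dropping subjects who already met the criterion would hide further widening in them, for instance from 130 to 170 ms, and would shrink denominators that are already tiny. That is correct, and the fix below avoids it.

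**Conclusion.** The point holds as a defect in how one descriptive ECG table is built. The QRS and PR rows cannot separate new from pre-existing findings. For QRS, the protocol itself admits subjects at the PCI cut-off; for PR, the case rests only on the absence of an entry limit. One affected subject moves an arm of 3 or 4 by 33 or 25 points, and an arm of 20 by 5. That size does not depend on prevalence; how likely it is to occur does, and any prevalence is an assumption.

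Three stronger readings are not supported. A reader might infer that pre-existing conduction delay enters the safety endpoint as an event; it does not, because these are PCI values and not adverse events. A reader might infer that the trial would show a false drug effect or mask a real one; no inference is drawn from this table, and the listings allow Baseline status to be recovered. A reader might also pair the 25-point shift with the 43-69% probability; the first is per arm and the second is for the whole trial. At the same 5-10% assumption, the matching figure for a given arm of 4 is 19-34%.

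**What to change.** Keep the existing overall PCI count. For QRS and PR, add two rows beneath it:

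- criterion not met at Baseline, with subjects below the cut-off at Baseline and at least one post-Baseline ECG as the denominator;
- criterion already met at Baseline, showing each subject's change from Baseline so that further widening stays visible.

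Alternatively, add a shift table from Baseline to the maximum post-Baseline value at the 120 ms and 220 ms cut-offs. Leave the QTc rows as they are.

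The cost is a sentence in SAP Section 14.4 or a footnote to Table 5, a few table rows and a small program change. Baseline is already defined in SAP Section 5.3 and Baseline ECGs are scheduled, so no new data are needed. The protocol prescribes no PCI rule for QRS or PR, so nothing in it conflicts.
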